13.5.3 Statistical methods for the continuous or graded endpoints

Continuous or graded responses, including changes from baseline in WOMAC Function and patient response, as well as KOOS and BPI items, will be analyzed in a repeated-measures analysis of covariance model with treatment, Study Day and their interactions as the main factors and the baseline value of the endpoint as a covariate. Missing data will not be imputed before such analyses. Within this model, t-tests will be used to compare the two XT-150 doses to placebo, with step-down Dunnett-like adjustments for multiplicity of doses. Within such models, changes from baseline may be analyzed at other time points (Days 7 [±1 day], 30 [±2 days], 60 (±7 days), 90 [±7 days], 120 [±7 days], and 150 [±7 days]). Additional efficacy analyses may be performed using alternate models.

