#### Efficacy:

The primary efficacy outcome measure is whether the subject achieves at least a 30% improvement from baseline in WOMAC Pain Score (obtained from the KOOS questionnaire) at Day 180, as recorded on a 0 to 20 point scale with 20 being the maximum (worst) score.

Secondary efficacy outcome measures are:

- Change from baseline in the WOMAC Function Score (from KOOS questionnaire) at Day 180
- Change from baseline in the WOMAC Pain Score (from KOOS questionnaire) at Day 180 (this endpoint was inadvertently omitted from the protocol)
- Change from baseline in patient response at Day 180, using a scale of 1 5, to the
  OA question: "Considering all the ways the OA in your knee affects you, how are
  you doing today?", with 1 being very good (asymptomatic and no limitation of
  normal activities) to 5, very poor (very severe, intolerable symptoms and inability
  to carry out normal activities)

Additional endpoints include:

CONFIDENTIAL Page 10 of 27

Final 2.0, 11 Oct 2021

Protocol No.: XT-150-2-0204 Sponsor: Xalud Therapeutics, Inc.

[figure not shown]

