#### 9.3. Efficacy Analysis

All inferential analyses of efficacy will be based on the first 180 days after dose administration (Stage A) and on the analysis of time from Day 0 until patient request for a second injection.

CONFIDENTIAL Page 18 of 27

Final 2.0, 11 Oct 2021

Sponsor: Xalud Therapeutics, Inc.

Protocol No.: XT-150-2-0204

[figure not shown]
For the statistical analysis of the primary efficacy endpoint, a logistic regression (response: 30% improvement at Day 180 (yes/no)) will be performed to compare 150 µg XT-150 with placebo and 450 µg XT-150 with placebo statistically. The model will include a fixed effect for treatment and the subject's baseline WOMAC pain score as a covariate. From this model, the 150 µg XT-150 to placebo and 450 µg XT-150 to placebo odds ratio of reduction and its two-sided 95% CI will be calculated. In this analysis, a subject who does not provide a response at Day 180 will be considered a non-responder (i.e., improvement will be set to "no").

In the event that one or more treatment arms has no responders, which would cause numerical difficulties in the logistic regression model, the statistical analysis will add 2 successes and 2 failures to each treatment group. This based on the recommendation in Agresti and Caffo, "Simple and Effective Confidence Intervals for Proportions and Differences of Proportions Result from Adding Two Successes and Two Failures," The American Statistician, Vol. 54, No. 4 (Nov., 2000), pp. 280-288.

The change from baseline in WOMAC Function Score will be analyzed using a repeated measures model including fixed effects for treatment (i.e., 150 µg XT-150, 450 µg XT-150, placebo), study day (i.e., Day 7, 30, 60, 90, 120, 150, 180) and treatment by study day interaction. In addition, the subject's baseline score will be included as a covariate. From the model, the treatment differences between 150 µg XT-150 and placebo, and 450 μg XT-150 and placebo will be estimated for the average effect of the first 180 days after dose administration (i.e., Stage A). Additionally, p-values and corresponding two-sided 95% confidence intervals will be provided.

The change from baseline in WOMAC Pain Score will be analyzed similarly.

Change from baseline in total and individual BPI, change from baseline in KOOS, and change from baseline in the patient response will be analyzed similarly.

CONFIDENTIAL Page 19 of 27

Final 2.0, 11 Oct 2021

Protocol No.: XT-150-2-0204 Sponsor: Xalud Therapeutics, Inc.

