#### **WOMAC Pain Score Change from Baseline**

WOMAC Pain Score Change from Baseline will be summarized with summary statistics by visit and treatment group. Analyses will be performed for both the ITT population and mITT population.

A Mixed Model analysis will be conducted and mixed model statistics (LSMean, StErr, LSMeans Diff and 95% CI of LSMeans diff) – generated for Day 180 and Day 360 (covariates include site, baseline WOMAC Pain, K/L and sex). The effect size at Day 180 and Day 360 using Cohen's d will be calculated from the observed mean and standard deviations and presented.

A summary line plot of WOMAC Pain Mean Change from Baseline by visit and treatment group (with Standard Error at each visit) will be generated.

The following additional exploratory analyses will be performed for the WOMAC Pain Change from Baseline using the same MMRM model to compare treatment groups:

• Stage B (Day 360) analyses comparing treatment groups placebo/150 and placebo/450 to assess the difference between these groups and the assumption of combining them for the placebo/active treatment group.

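### The repeated-measures models in SAP 9.3 fit one baseline slope to all visits from Day 7 to Day 180; if the link to baseline fades, this costs a modest amount of precision that one extra model term would recover

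*SAP*

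**What the plan says.** SAP 9.3 describes the model for change in WOMAC Function. Its fixed effects are treatment, "study day (i.e., Day 7, 30, 60, 90, 120, 150, 180) and treatment by study day interaction". It continues: "In addition, the subject's baseline score will be included as a covariate". WOMAC Pain, BPI, KOOS and the patient response to the OA question are analysed in the same way.

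Protocol 13.5.3 specifies the same structure, "with treatment, Study Day and their interactions as the main factors and the baseline value of the endpoint as a covariate". The only interaction in either document is between treatment and study day. Neither states a covariance structure, and neither gives a standard deviation or a correlation between visits.

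The two documents differ on which contrast is taken. The SAP's secondary endpoints are set at Day 180, for example "Change from baseline in the WOMAC Function Score (from KOOS questionnaire) at Day 180". SAP 9.3, however, says the treatment differences "will be estimated for the average effect of the first 180 days after dose administration (i.e., Stage A"). The protocol adds "Within such models, changes from baseline may be analyzed at other time points", which implies that Day 180 is its default contrast. The SAP Addendum, which is post hoc, asks for both late visits: mixed-model statistics are "generated for Day 180 and Day 360 (covariates include site, baseline WOMAC Pain, K/L and sex").

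**The concern.** A baseline covariate with no visit interaction forces the same regression on baseline at every visit. KOOS asks about the last week. Day 7 therefore reports the week just after the baseline assessment, and Day 180 reports a week six months later. It is plausible that the second is less closely tied to baseline than the first. One slope then corrects too little for chance baseline imbalance at early visits and too much at late ones. Baseline is in the model to gain precision, and part of that gain is lost at the visit where the secondary endpoints are defined.

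**Working it through.** **The plan's own figure.** The documents give no power or precision figure for these models. The only design figure is for the binary primary endpoint: 95% power for at least one arm and 85% for both, with 90 per arm and 30% v 10% responders (Protocol 13.1, Table 7). Exact binomial enumeration with Fisher tests and the protocol's step-down Dunnett critical values (2.212, then 1.96) gives 94.9% and 83.4%. A logit Wald test gives 96.2% and 87.5%. The stated figure is reproduced closely. It comes from a single-visit analysis that has no common slope across visits.

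**Inputs.** From the documents: seven post-baseline visits, 90 per arm, and the model terms above. Assumed: complete data, equal standard deviations at all visits (set to 1), correlation between two visits of a + c·exp(−days/τ), and a Stage A average that weights the seven visits equally.

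**Formulas.** The adjusted difference at a visit is the raw difference minus b times the baseline difference, where b is the common slope. Working with change scores shifts every slope by −1 and alters nothing else.
- Visit-specific slope at Day 180: r, the correlation of Day 180 with baseline.
- Common slope under an unstructured fit: b = w′r, where the vector r holds the seven visit slopes, w = S⁻¹1/(1′S⁻¹1), and S is the covariance of the visits given baseline.
- Variance at Day 180, up to a constant: 1 − r² with its own slope, and 1 + b² − 2br with the common slope.
- Excess variance: (b − r)²/(1 − r²).
- For the Stage A average, the excess is (b − mean slope)²/Var(average given baseline).

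**One pattern in full (a = 0.2, c = 0.6, τ = 90).**
- The visit slopes are 0.755, 0.630, 0.508, 0.421, 0.358, 0.313 and 0.281. Their mean is 0.467.
- The unstructured fit gives b = 0.585, with 62% of the weight on Days 7 and 30.
- Day 180: (0.585 − 0.281)²/(1 − 0.281²) = 0.0924/0.921 = 10.0% excess variance. That is √1.100 = 1.049, or 4.9% in standard error. A simulation of 4,000 trials of 3 × 90 gave 4.5%, with bias about zero in both models.
- Stage A average: (0.585 − 0.467)²/0.337 = about 4%.
- Equal visit weights: b = 0.467, so the Day 180 excess is (0.467 − 0.281)²/0.921 = 3.7%. For the average it is exactly zero, because the common slope is then the average slope.
- Unadjusted change score: variance 2(1 − 0.281) = 1.44. Common slope: 1 + 0.585² − 2(0.585)(0.281) = 1.01. Own slope: 0.92.

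**Range of excess variance.**

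| a, c, τ | r at Day 7 → Day 180 | b | Day 180 | Stage A average | Day 180, equal weights |
|---|---|---|---|---|---|
| 0.6, 0, any | 0.60 → 0.60 | 0.60 | 0% | 0% | 0% |
| 0.5, 0.3, 90 | 0.78 → 0.54 | 0.69 | 3% | 1% | 1% |
| 0.4, 0.4, 90 | 0.77 → 0.45 | 0.66 | 5% | 2% | 2% |
| 0.3, 0.5, 90 | 0.76 → 0.37 | 0.62 | 7% | 3% | 3% |
| 0.2, 0.6, 90 | 0.76 → 0.28 | 0.59 | 10% | 4% | 4% |
| 0.15, 0.75, 90 (steep) | 0.84 → 0.25 | 0.69 | 20% | 12% | 6% |

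**Sensitivity to equal SDs.** Take the pattern worked in full and let the SD grow steadily to 1.4 times baseline by Day 180. The Day 180 slope becomes 1.4 × 0.281 = 0.394 and the common slope 0.675. The excess is (0.675 − 0.394)²/(1.96 − 0.394²) = 0.079/1.805 = about 4%, instead of 10%.

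**In participants.** An excess of 3% to 10% at Day 180 is equivalent to 90/1.03 = 87 down to 90/1.10 = 82 per arm.

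**The case against.** The strongest reply is that the loss is not established. It needs a baseline slope that falls over time. For early visits to dominate, it also needs an unstructured-type fit. The documents settle neither. With equal visit weights, Days 7 and 30 carry only 2/7 = 29% of the slope. This stands, and it is why every figure here is conditional.

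Second, SAP 9.3 takes the Stage A average from this model, not the Day 180 difference, and for the average the loss is small or nil. This stands for SAP 9.3 as written. Day 180 still matters, because the secondary endpoints are defined there, the protocol's default contrast is there, and the addendum reports it.

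Third, little hangs on it. Protocol 13.5.1 lets p-values for other endpoints be read as descriptive, and Protocol 13.5.3 allows alternate models. That lowers the severity but does not remove the gain in the estimates and confidence intervals.

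A reader might go further and infer that the adjustment is no better than none. In the pattern worked in full, the common-slope variance of 1.01 is indeed about that of the raw Day 180 score (1.00). But the endpoint is change from baseline, whose unadjusted variance is 1.44, and the planned model improves clearly on that. A reader might also infer bias. With randomised arms and complete data, the common slope affects precision only.

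**Conclusion.** The point holds as a minor, conditional loss of precision. As written, SAP 9.3 and Protocol 13.5.3 impose one baseline slope on Days 7 to 180 for all continuous or graded endpoints. If the link to baseline fades, excess variance is roughly 3% to 10% for the Day 180 contrast and about 1% to 4% for the Stage A average. Steep decay raises these to about 20% and 12%. Equal visit weights reduce them to 1% to 6% and nil. A constant correlation gives none.

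These figures rest on assumed correlations, complete data and, except where stated, an unstructured covariance and equal SDs. Protocol 13.5.3 rules out imputation before these analyses. Dropout was not modelled, so the statement of no bias covers complete data only. The primary endpoint and its stated power do not change.

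**What to change.** Add a baseline-by-study-day interaction to the repeated-measures model in SAP 9.3 for WOMAC Function, WOMAC Pain, BPI, KOOS and the patient response, so that each visit has its own baseline slope. The cost is 6 degrees of freedom (seven slopes instead of one) with about 270 participants, plus a wording change. No new data are needed. If the slopes turn out equal, almost nothing is lost. Naming the covariance structure in the same sentence would also settle how visits are weighted.

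The addendum's mixed models could take the same term. The addendum states that its analyses were defined after the database was locked and unblinded, so a change there would be post hoc and should be labelled supportive. The same label would apply to any refit of the SAP 9.3 models made after that point.

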11.0 ASSESSMENT OF EFFICACY PARAMETERS

Efficacy assessments will be recorded throughout the study (up to Study Day 360) per the Schedules of Assessments and Procedures in Table 1 and Table 2.

The primary efficacy outcome measure is:

 Whether the subject achieves at least a 30% improvement from baseline in WOMAC Pain Score at Day 180, as recorded on a 0 to 20 point scale with 20 being the maximum (worst) score

Secondary efficacy outcome measures:

- Change from baseline in the WOMAC Function Score at Day 180
- Change from baseline in patient response, at Day 180, to the question:
 "Considering all the ways the OA in your knee affects you, how are you doing today?", using a scale of 1 5, with 1 being very good (asymptomatic and no limitation of normal activities) to 5, very poor (very severe, intolerable symptoms and inability to carry out normal activities)

Additional outcome measures include:

- Total and individual parameter scores for the Brief Pain Inventory of Intensity and Interference (BPI)
- The Knee Outcome and Osteoarthritis Scores (KOOS)

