13.5 Analysis of Efficacy

All inferential analyses of efficacy will be based on the first 180 days after dose administration (Stage A) and on the analysis of time from Day 0 until patient request for a second injection (see Section 13.5.4). Other analyses of data from Stage B and comparisons between Stage A and B will be descriptive; such analyses will be specified in the SAP.

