#### 9. EFFICACY DATA

#### 9.1. Efficacy Assessments

Efficacy assessments will be recorded throughout the study, during Stage A and Stage B at each of the following study visits:

Stage A: nominally Days 7, 30, 60, 90, 120, 150, and 180.

Stage B: nominally Days 210, 240, 270, 300, 330 and 360

The primary efficacy outcome measure is whether the subject achieves at least a 30% improvement from baseline in WOMAC Pain Score (obtained from the KOOS questionnaire) at Day 180, as recorded on a 0 to 20 point scale with 20 being the maximum (worst) score.

Secondary efficacy outcome measures are:

- Change from baseline in the WOMAC Function Score (from KOOS questionnaire) at Day 180
- Change from baseline in the WOMAC Pain Score (from KOOS questionnaire) at Day 180 (this endpoint was inadvertently omitted from the protocol)
- Change from baseline in patient response at Day 180, using a scale of 1 5, to the
  OA question: "Considering all the ways the OA in your knee affects you, how are
  you doing today?", with 1 being very good (asymptomatic and no limitation of
  normal activities) to 5, very poor (very severe, intolerable symptoms and inability
  to carry out normal activities)

Additional endpoints include:

Final 2.0, 11 Oct 2021

Protocol No.: XT-150-2-0204 Sponsor: Xalud Therapeutics, Inc.

- Total and individual parameter scores for the Brief Pain Inventory of Intensity and Interference (BPI) (reported values and change from baseline)
- The Knee Outcome and Osteoarthritis Scores (KOOS) (reported values and change from baseline)

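### The secondary endpoints are defined as change at Day 180, but the only treatment difference named for them in the visible text of SAP 9.3 is the average over Stage A

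*SAP*

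**What the plan says.** **Endpoint definitions.** SAP 4.6 and 9.1 fix all three secondary endpoints at one visit. They list "Change from baseline in the WOMAC Function Score (from KOOS questionnaire) at Day 180", the matching WOMAC Pain change (which the SAP says the protocol left out by oversight), and "Change from baseline in patient response at Day 180". Protocol 11.0 sets the same time point for two of them: "Change from baseline in the WOMAC Function Score at Day 180", and the OA question.

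**Protocol analysis.** Protocol 13.5.3 specifies a repeated-measures analysis of covariance with treatment, study day and their interaction. It says "Within this model, t-tests will be used to compare the two XT-150 doses to placebo", with step-down Dunnett-like adjustment for two doses. It then adds "Within such models, changes from baseline may be analyzed at other time points" and lists Days 7 to 150. Day 180 is therefore the implied main contrast, although the section does not say so outright.

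**SAP analysis.** SAP 9.3 keeps that model. For WOMAC Function, the dose-versus-placebo differences "will be estimated for the average effect of the first 180 days after dose administration", and p-values and two-sided 95% intervals follow. WOMAC Pain and patient response are to be handled in the same way. No visit weights are given. The visible text of SAP 10 records one change from the protocol, the dropping of step-down testing.

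**Addendum.** Its Treatment Groups section compares each dose with placebo at Day 180 for Stage A. Its sections on WOMAC Pain and WOMAC Function give mixed-model differences at Day 180 and Day 360, adjusted for site, baseline score, Kellgren-Lawrence grade and sex. It states that it was written after database lock and unblinding and is post hoc. Its visible endpoint list does not include patient response.

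**The concern.** A reader of the report will expect the result for a Day 180 endpoint to be a Day 180 difference. If SAP 9.3 is followed as its visible text stands, the estimate, interval and p-value describe the mean effect over Days 7 to 180.

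The protocol's own rationale makes a changing effect plausible. Section 4.1 describes one injection of a plasmid intended for transient expression, with protein produced over the weeks that follow. Day 180 asks whether benefit lasts six months. An average can be clearly positive when nothing remains at Day 180, and it dilutes an effect that is still building.

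**Working it through.** The documents give no SD, correlation, effect profile, visit weights or power for the secondary endpoints, so there is no stated figure to reproduce.

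**Inputs from the documents:** 90 per group (Protocol 13.1); visits on Days 7, 30, 60, 90, 120, 150 and 180 (SAP 9.3).

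**Assumptions:** common SD, equal correlation ρ of 0.5 to 0.7 between visits, no missing data, normal approximation, two-sided 0.05 without dose adjustment, peak effect 0.4 SD.

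**Step 1: weight of Day 180 in the average.** Equal weights: 1/7 = 14%. Time (trapezoid) weights over Days 7-180: 15/173 = 9%.

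**Step 2: what the average estimates.** The mean visit day is 637/7 = 91 with equal weights and (7 + 180)/2 = 93.5 with time weights.

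| Ramp starts at | Fading to zero at Day 180: average / initial effect | Growing to Day 180: average / Day 180 effect |
|---|---|---|
| Day 0, equal weights | 1 − 91/180 = 0.494 | 91/180 = 0.506 |
| Day 0, time weights | 1 − 93.5/180 = 0.481 | 93.5/180 = 0.519 |
| Day 7, equal weights | 1 − 84/173 = 0.514 | 84/173 = 0.486 |
| Day 7, time weights | 1 − 86.5/173 = 0.500 | 86.5/173 = 0.500 |

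The range is 48-52%. With a constant effect the ratio is 1 for any weights that sum to 1.

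**Step 3: precision.** The standard error of a single-visit difference is √(2/90) = 0.149 SD. With equal weights, the standard error of the average is √((1 + 6ρ)/7) times that: 0.756, 0.811 and 0.862 for ρ = 0.5, 0.6 and 0.7. Time weights give 0.760, 0.814 and 0.864.

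**Step 4: probability of rejection,** Φ(effect/SE − 1.960), with equal weights and ramps from Day 0. For example, a constant effect at ρ = 0.5 gives 0.4/(0.149 × 0.756) = 3.55, and Φ(1.59) = 0.94. At Day 180, 0.4/0.149 = 2.68, and Φ(0.72) = 0.77.

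| Profile (peak 0.4 SD) | Effect at Day 180 | Average effect | Rejection, Day 180 | Rejection, average |
|---|---|---|---|---|
| Constant | 0.40 | 0.40 | 0.77 | 0.88-0.94 |
| Fading to zero | 0 | 0.198 | 0.05 (the test level) | 0.34-0.42 |
| Growing | 0.40 | 0.202 | 0.77 | 0.35-0.43 |

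Time weights change the last column little: 0.87-0.94, 0.32-0.40 and 0.36-0.45.

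**Step 5: dose adjustment.** With a single-step Dunnett critical value of 2.212, the average gives 0.82-0.91 (constant), 0.25-0.32 (fading) and 0.26-0.34 (growing). The Day 180 contrast gives 0.68 where the Day 180 effect is 0.4 SD.

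**The case against.** **The average has a basis in the protocol.** Section 13.5 rests inference on the first 180 days, and 6.2 evaluates endpoints at each visit and overall. Protocol 11.0 lists outcome measures without naming a contrast, and 13.5.3 only implies Day 180. This stands, so the visible silence of SAP 10 is a weak complaint. It justifies reporting the average as well, not in place of the endpoint as defined.

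**The model already contains the answer.** The interaction term yields the Day 180 difference. True, but the visible text of 9.3 does not direct that it be reported. The by-visit summaries in SAP 9.2 are descriptive, and the sentence covering WOMAC Function does not mention treatment group.

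**The addendum covers it.** Partly. It supplies Day 180 differences for Pain and Function, but post hoc and with other covariates, and its visible text gives none for patient response.

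**Little depends on it.** Protocol 13.5.1 allows p-values for other endpoints to be read as descriptive, the primary responder analysis is at Day 180, and linear ramps are extreme cases. All of this limits the consequence. A descriptive estimate should still describe the endpoint named.

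**Stronger readings that the documents do not support.** A reader might infer that no Day 180 contrast was planned before unblinding, or that the one for WOMAC Pain was first named afterwards. The visible text cannot show either. The contents page lists a section 11.1 on the unblinded analysis after Stage A whose text is not visible, and the table list in Appendix 2 is not visible; either could name the contrast. A reader might also call the rejections under a fading effect false positives. They are correct for the average and mislead only if reported as Day 180 results.

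**Conclusion.** The mismatch is real in the visible text: three endpoints defined at Day 180, and one named treatment difference that averages over Stage A with unstated weights. It should be put right in reporting. It does not threaten the primary analysis or any test with error control in the visible text.

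Its size depends on an effect profile that the documents do not give. A constant effect costs nothing in meaning and favours the average for power. Linear fading or growth makes the average about half of the peak effect. The ratios in Step 2 rest only on the linear profiles and the visit weights. The power figures rest also on the assumed 0.4 SD, the correlation range and no dropout.

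**What to change.** By a dated note or in the study report, without rewriting 9.3 of the final SAP:

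1. For WOMAC Function, WOMAC Pain and patient response, present the Day 180 treatment-by-study-day contrast against placebo from the existing 9.3 model as the result for the defined endpoint. Give the estimate, 95% interval and p-value, and state whether they are adjusted for two doses. Protocol 13.5.3 called for such an adjustment, and SAP 10 drops the step-down form.
2. Keep the Stage A average beside it, labelled as supportive, with its visit weights stated.
3. Have the sponsor check the unredacted SAP, including 11.1 and Appendix 2, and then state accurately when each contrast was first named. The addendum places database lock and unblinding in the past, so a note written now should say that it comes after both.

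**Cost:** no new data and no new model, only a short note or paragraph and one set of table rows. The Day 180 contrast is less precise: the average's standard error is 0.76-0.86 of it under the assumptions above. The power lost if the effect is constant is the reason to keep the average in view.
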